# Table 10 Expansion Part: Objectives and Endpoints

Objectives	Endpoints
Primary	
Evaluate anti-tumor activity	Objective response rate (ORR) based on RECIST v1.1
Secondary	
Evaluate anti-tumor activity based on response assessment criteria RECIST v1.1	
 
Anti-tumor activity, ie, reduction in tumor size according to response assessment criteria RECIST v1.1:
 
Disease control rate (DCR)
 
Duration of response (DOR)
 
Time to response (TTR)
 

Evaluate efficacy	

Progression free survival (PFS)

Overall survival (OS)

• Further describe the safety profile of GEN1044	Adverse events (AEs) and safety laboratory parameters
Further describe the PK profile	• PK parameters (clearance; volume of distribution; area under the concentration-time curve (AUC) from time zero to last quantifiable sample (AUC last ) and from time zero to infinity (AUC inf ); maximum (peak) observed serum drug concentration (C max ); time to reach maximum (peak) serum drug concentration (T max ); predose trough concentrations (C Trough ); and elimination half-life (T 1/2 ).
Further describe the immunogenicity of GEN1044	Anti-drug antibody (ADA) response
Exploratory	
Assess pharmacodynamics and potential biomarkers of GEN1044	• Immune system activation (eg, T-cell activation and proliferation, cytokine production, and expression of tumor targets (eg, 5T4, and potential biomarkers),
Assess anti-tumor activity based on iRECIST	Anti-tumor activity, ie, reduction in tumor size according to iRECIST  Immune ORR (iORR)  Immune iDCR (iDCR)  Immune DOR (iDOR)  Immune PFS (iPFS)
For prostate cancer subjects only: Assess antitumor activity based on Prostate Cancer Working Group 3 (PCWG3)-Modified Response Evaluation Criteria in Solid Tumors (mRECIST) 1.1      For prostate cancer subjects only: Assess changes in prostate-specific antigen (PSA) from baseline	
 
Anti-tumor activity, ie, reduction in tumor size according to RECIST v1.1 modified by PCWG3 for bone lesions
 
Modified ORR (mORR)
 
Modified DCR (mDCR)
 
Modified DOR (mDOR)
 
Composite response rate (CRR)
 
Radiographic progression-free survival (rPFS)
 
PSA response
 
PSA progression
 

Document Number: TMF-34513

Version: 4.0

### 4 TRIAL DESIGN

# 4.1 Description of Trial Design

This is a first-in-human (FIH), open-label, multinational, multicenter phase 1/2a trial to evaluate the safety, PK, pharmacodynamics, and preliminary efficacy of GEN1044. GEN1044 will be administered as an IV infusion to a mixed population of subjects with solid tumors. The trial consists of 2 consecutive parts: a Dose Escalation (phase 1) and an Expansion (phase 2a).

In the Dose Escalation part, subjects will be administered GEN1044 according to dose levels outlined in Section 4.2. In the Expansion part, subjects will be administered GEN1044 with the recommended dose(s) from the escalation. GEN1044 will be administered via IV infusion weekly (Q1W) for the first 4 cycles (each cycle is 21 days), followed by every 3 weeks (Q3W), thereafter. Cycle 1 will consist of a priming dose, an intermediate dose, and a full dose. Alternatively, when necessary, Cycle 1 will consist of a priming and 2 intermediate doses, with the first full dose administered on Cycle 2 Day 1. The decision as to whether 1 intermediate dose or 2 intermediate doses will be used for a given cohort will be based on the recommendation of the DEC and confirmed by the Safety Committee (see Section 10.10).

In both parts, subjects will continue to receive GEN1044 until any of the protocol-defined treatment discontinuation criteria are met (refer to Section 8.1). Different doses and schedules might be explored during the Dose Escalation and/or Expansion parts based on the data generated in the dose escalation. Efficacy will be assessed by on-treatment radiological exams/imaging every 6 weeks (±7 days) for 36 weeks, and every 12 weeks (±7 days) thereafter until PD as assessed by the investigator, the start of new anti-cancer therapy, withdrawal of consent, or death, whichever occurs first. For subjects with prostate cancer, efficacy will also be assessed by on-treatment bone scans every 6 weeks (+7 days) (or longer per local standards) for 24 weeks, and every 12 weeks (±7 days) thereafter until PD, the start of new anti-cancer therapy, withdrawal of consent, or death, whichever occurs first. Response assessment criteria relevant to the tumor type (eg, RECIST v1.1 criteria) (Eisenhauer et al., 2009) will be used for response evaluation. Images may be submitted to a central imaging vendor if additional analyses are conducted.

For subjects in the Dose Escalation part who receive GEN1044 doses beyond the DLT evaluation period, all AEs corresponding to the definition of DLT (see Section 7.1) will be considered for the purpose of determining the RP2D. For the selection of the recommended dose for treatment of the Expansion cohorts and for further development, all drug-related AEs will be taken into consideration.

The concept of the design of the trial is shown in Section 1.2, Figure 1 . The Dose Escalation part will consist of dose-level (DL) cohorts. The Expansion part will consist of parallel cohorts, by type of cancer.

[figure not shown]
### **4.2 Dose Escalation Part**

The rationale for the starting dose selection is provided in Section 4.6.	

Version: 4.0

The rationale behind implementation of intermediate dose(s) is to mitigate potential AEs (including CRS).

The DLT period will extend from the first dose on C1D1 until 7 days after the first full dose:

The planned doses are:

- a priming dose of 0.3 mg or higher,
- a full dose,
- one, or potentially two, intermediate doses in-between the prime and full dose (if two intermediate doses are used the 1st will be lower than the 2nd). The DLT period will vary, depending on whether one or two intermediate doses are given (see above).

Higher dose levels might be explored depending on accrued data during the escalation part. All doses are fixed doses (not weight adjusted).

The FIH single-subject cohort is planned with a priming dose of 0.3 mg on C1D1, followed by a full dose of 3.0 mg on C1D8 and C1D15.

In the escalation part, the cohort sizes will start with single-subject cohorts. The trigger point to expand a 1-subject cohort into a 3-subject cohort is the observation of any of the following events:

- A grade  $\geq 2$  AE is observed within the DLT period.
- A DLT (see Section 7.1) is observed at any time within the DLT period.

That is, when any of these events occur in a 1-subject cohort, it is expanded by 2 additional subjects. When those subjects have completed their DLT period, the escalation model in Section 4.2.1 is initiated. If the single-subject cohorts reach the maximum dose level (beyond which no escalation is possible), it will be mandatory to expand that cohort size to 3 subjects.

In addition, in the single subject-cohort phase, the next cohort can start only once the DLT period for the previous dose level has been assessed and the next dose level is proposed by the DEC and endorsed by the SC. The DEC will recommend the dose level for the next cohort of subjects to the SC and this will need to be endorsed by the SC prior to using the recommended or higher dose in the next cohort dose level implementation. To supplement routine safety monitoring by the sponsor SC as outlined in this protocol, a DMC will monitor safety data for the trial on a quarterly basis or more frequently as determined by the sponsor. Additional details regarding the DEC, sponsor SC, and the DMC can be found in Section 10.9 and in Section 10.10.

If any single-subject DL cohort is expanded to a total of 3 subjects (based on the trigger point above being reached), all subsequent DL cohorts will initially have 3 subjects per cohort.

Version: 4.0

The next DL cohort, possibly including a higher full-dose level, can start only once the DLT period for the previous DL cohort has been assessed and the next full-dose level is proposed by the DEC and endorsed by the SC. Parallel cohorts may be initiated at any time, provided the full-dose level of the parallel cohort has already been safety-cleared by the SC and does not equal or surpass the full-dose level in the DL cohort under investigation. The DEC will recommend the full-dose level for the next cohort of subjects, including whether 1 or 2 intermediate doses should be given, to the SC and this will need to be endorsed by the SC prior to using the recommended or higher full-dose in the next cohort dose level implementation. The descriptive DLT tables provided to the DEC (see Appendix 9) will provide an overview of the DLT rates considering the whole DL cohort (as intended in the original protocol), and considering the individual period-specific dose level.

For any DL cohort that enrolls more than 1 subject, there will be a minimum of 24 hours between an individual subject's treatment infusion stop and a subsequent subject's treatment start in the same cohort, to account for any acute safety signals in each new dose level. The 24-hour treatment window between same-cohort subjects will not apply to backfilling cohorts enrolling subjects to be exposed to previously safety-cleared full dose levels.

An overnight stay (24 hours in-hospital observation) will be required for all subjects after administration of GEN1044 on Day 1 and Day 8 during Cycle 1 only and may be required for additional subjects and/or dose levels if recommended by the sponsor SC. If a second intermediate dose is implemented at C1D15, the sponsor may decide to require additional 24-hour hospitalization following this dose administration.

During treatment in the Dose Escalation part, safety assessments will be performed as indicated on Table 1. For the assessments of each cohort, the dose-limiting toxicities (DLTs) will be collected for the first treatment cycle, ie, a DLT evaluation period of 21 days from the priming dose (or 28 days if two intermediate doses are applied).

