#### 1.3 Schedule of Activities

Table 1 through Table 8 list all of the assessments and indicate with an "X" the evaluations performed by visit.

- Table 1: Visit Evaluation Schedule Dose Escalation Part
- Table 2: PK, ADA and ECG Sampling Dose Escalation Part
- Table 3: Vital Signs Dose Escalation Part
- Table 4: Biomarker Table Dose Escalation Part
- Table 5: Visit Evaluation Schedule Expansion Part
- Table 6: PK, ADA and ECG Sampling Expansion Part
- Table 7: Vital Signs Expansion Part
- Table 8: Biomarker Table Expansion Part

In addition to the fixed visits, it may be necessary to perform some of the assessments at unscheduled time points if deemed clinically necessary by the investigator. All data obtained from these assessments must be supported in the subject's source documentation.

Document Number: TMF-34513

**Table 1** Visit Evaluation Schedule – Dose Escalation Part

Treatment Cycle (C)	Notes	Section Reference	Screening					Cycl	e 1							Cycle	2		
Day (d)/Week (wk)			≤ 28d prior to C1 (1d)	1d	2d	4d	8d	9d	11d	15d	16d	18d	1d	2d	4d	8d	9d	11d	15d
Visit window							+1d			+1d			+2d			+2d			+2d
Informed Consent		13.2.3	X																
Eligibility Criteria		5.1, 5.2	X																
Demographics		9.1.1	X																
Medical History		9.1.2 to 9.1.5	X																
Body weight		9.3.2	X																
Physical Examination	After Screening, perform exam only as indicated by subject's symptoms, AEs, or findings as determined by investigator.	9.3.1	X	X			X			X			X			X			X
Vital Signs	See Table 3 for GEN1044 dosing days. At Unscheduled visit, perform only as indicated by subject's symptoms, AEs, or findings as determined by investigator.	9.3.3	X	X			X			X			X			X			X
ICE Score Assessment	See Table 18.	10.4.2	X	X			X			X			X						
ECG	See Table 2	9.3.4	X																
Radiological Exam/Tumor Imaging	Imaging is calendar based. On-treatment imaging every 6 wks (±7d) for the first 36 wks (calculated from C1D1), then every 12 wks (±7d) until PD, start of new anticancer therapy, consent withdrawn, or death, whichever occurs first.	9.2.1	Xª																
Whole-body Bone Scan	Subjects with prostate cancer. Ontreatment scans every 6 wks (±7d) (or longer per local standards) for the first 24 wks(calculated from C1D1), then every 12 wks (±7d) until PD, start of new anticancer therapy, consent withdrawn, or death, whichever occurs first.	9.2.1	X																

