# **Table 3** Vital Signs – Dose Escalation Part

Notes	Section Reference	Time Point
	9.3.3	Pre-infusion (up to 30 min before infusion)
		15 min after start of infusion (±5 min)
If infusion lasts for more than 60 minutes, vital signs should be assessed every 15 minutes (± 5 minutes) for the remaining duration of the infusion		At the end of infusion (±5 min)
		30 min after end of infusion (±5 min)
	·	1 hour after end of infusion (±10 min)
		2 hours after end of infusion (±10 min)

 Table 4
 Biomarker Table – Dose Escalation Part

[figure not shown]

 Table 4
 Biomarker Table – Dose Escalation Part (Continued)

Document Number: TMF-34513

 Table 5
 Visit Evaluation Schedule – Expansion Part

Treatment Cycle (C)	Notes	Section Reference	Screening					Сус	le 1							Cycle	2		
Day (d)/Week (wk)			≤28d prior to C1 (1d)	1d	2d	4d	8d	9d	11d	15d	16d	18d	1d	2d	4d	8d	9d	11d	15d
Visit window							+1d			+1d			+2d			+2d			+2d
Informed Consent		13.2.3	X																
Eligibility Criteria		5.1, 5.2, 9.4.2	X																
Demographics		9.1.1	X																 
Medical History		9.1.2 to 9.1.5	X																
Body weight		9.3.2	X																
Physical Examination	Full physical exam at Screening. After Screening, perform exam only as indicated by subject's symptoms, AEs, or findings as determined by investigator.	9.3.1	X	X			X			X			X						X
Vital Signs	Full vital signs only at Screening; for subsequent visits, only temperature and blood pressure. See Table 7 for GEN1044 dosing days. At Unscheduled visit, perform only as indicated by subject's symptoms, AEs, or findings as determined by investigator.	9.3.3	X	X			X			X			Х						X
ICE Score Assessment	See Table 18.	10.4.2	X	X			X			X			X						
ECG	See Table 6	9.3.4	X																
Radiological Exam/Tumor Imaging	See footnote "a" regarding Screening. Imaging is calendar based. On-treatment imaging every 6 wks (±7d) for the first 36 wks (calculated from C1D1), then every 12 wks (±7d) until PD, start of new anticancer therapy, consent withdrawn, or death, whichever occurs first.	9.2.1	Xª																
Whole-body Bone Scan	Subjects with prostate cancer. Ontreatment scans every 6 wks (±7d) for the first 24 wks (calculated from C1D1), then every 12 wks (±7d) until PD, start of new anti-cancer therapy, consent withdrawn, or death, whichever occurs first.	9.2.1	X																

Document Number: TMF-34513

Treatment Cycle (C)	Notes	Section Reference	Screening					Cyc	le 1							Cycle	2		

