#### 6.2 Premedication Prior to GEN1044 Administration

The purpose of the prophylactic premedication is to mitigate risk and severity of infusion-related reactions (IRRs) and CRS. Premedication with corticosteroids, antihistamines, and antipyretics (Table 12) is mandatory 30 to 120 minutes prior to the first 3 administrations of GEN1044 in Cycle 1, ie, the first, second, and third administrations in the Dose Escalation part and in the Expansion part. If CRS  $\geq$  grade 2 occurs following the third administration (C1D15), prophylactic premedication should be continued and administered at the fourth administration (C2D1) and onwards until CRS events do not occur. If a grade 1 CRS event or no CRS event occurs following the third administration (C1D15), then prophylactic premedication should not be administered for subsequent GEN1044 administrations.

Corticosteroid administration can be either IV or oral including pre-medication administration (Table 12) with the recommended dose or equivalent (Appendix 3).

Version: 4.0

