# **6.3** Dosages and Administration

Trial treatment should be administered as described in Section 4.2 (Dose Escalation) and Section 4.3 (Expansion) until one or more of the discontinuation criteria in Section 8.1 are met:

- Cycles 1 through 4: Days 1, 8, and 15 (once weekly for a 21-day cycle)
- Cycles 5 and beyond: Day 1 (every 3 weeks for a 21-day cycle)

Refer to the preparation and administration guideline for additional information and stepwise guidance on dosage and administration.

Detailed dose modification guidance is provided in Section 7. Refer to Section 6.5 for information regarding concomitant therapy.

GEN1044 will be administered using IV infusion on Days 1, 8, and 15 of each 3-week (21-day) treatment cycle. GEN1044 will be administered as a fixed dose. In the Dose Escalation part, subjects will be administered GEN1044 according to dose levels outlined in Section 4.2. In the Expansion part, subjects will be administered GEN1044 with the recommended dose from the escalation.

As a routine precaution, subjects dosed with GEN1044 must be monitored during infusion and treated in an area with resuscitation equipment and emergency agents. For weekly dosing during Cycle 1 and Cycle 2, all subjects must be observed for at least 4 hours after ending infusion of GEN1044. For all subsequent cycles, subjects must be observed for at least 2 hours after ending infusion of GEN1044. See Section 4.2 for additional details regarding when an overnight stay (24 hours in-hospital observation) is required.

Refer to the administration and preparation guideline in the GCT1044-01 IMP Manual for additional guidance on trial drug preparation, handling, and storage.

† or equivalent, including oral dose.

Version: 4.0

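### The 24-hour gap between subjects runs to treatment start and is not stated for the first full dose, so two subjects can receive an uncleared full dose on the same day

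*Protocol*

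**What the plan says.** Protocol 4.2 sets, for any dose-level (DL) cohort with more than one subject, "a minimum of 24 hours between an individual subject's treatment infusion stop and a subsequent subject's treatment start in the same cohort". The stated purpose is to catch acute safety signals in each new dose level. The only exemption is for "backfilling cohorts enrolling subjects to be exposed to previously safety-cleared full dose levels".

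The component being escalated is the full dose: "The DEC will recommend the full-dose level for the next cohort of subjects, including whether 1 or 2 intermediate doses should be given". Protocol 7.1 places the first full dose on C1D15 with one intermediate dose and on C2D1 with two. The visit-window row of Protocol Table 1 allows +1 day at C1D15 and +2 days at C2D1.

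Other protection on those days:

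- **Overnight stay (4.2).** By default it covers C1D1 and C1D8 only. The Safety Committee (SC) may extend it to further subjects or dose levels.
- **Observation (6.3).** In Cycles 1 and 2, "all subjects must be observed for at least 4 hours after ending infusion of GEN1044". Table 1 also schedules next-day visits (C1D16, C2D2).
- **Premedication (6.2).** It is mandatory for the first three administrations, so C1D15 is covered. If grade 1 CRS or none follows C1D15, "then prophylactic premedication should not be administered for subsequent GEN1044 administrations". A first full dose on C2D1 can therefore be given without it.

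**The concern.** The gap ends at the start of the next subject's treatment, which most naturally means C1D1. The dose given that day is the priming dose, which is 1 mg in 8 of the 9 sequences in SAP Table 1. A gap applied only there would rarely separate exposures to a dose that is new. The new exposure comes two or three weeks later, and by then the visit windows can close the spacing set at C1D1.

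Patient safety is at stake. A second subject could be infused with a full dose the SC has not cleared before 24 hours of data exist from the first subject given it. Preventing that is the purpose of the gap. A site acting on the natural reading would record no deviation.

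**Working it through.** **1. Day of first full dose.** Protocol 4.2 and 7.1 end the DLT period 7 days after the first full dose. Counting inclusively, 15 + 7 − 1 = 21 days for C1D15 and 22 + 7 − 1 = 28 days for C2D1. Both match 7.1, so the two dosing days are confirmed.

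**2. Permitted days.** Call the first subject's C1D1 day 0, and count windows from each subject's own C1D1. A subject starting on day *d* may receive the first full dose on days *d*+14 to *d*+15 (C1D15) or *d*+21 to *d*+23 (C2D1). Two subjects starting *g* days apart can share a day only if *g* is no larger than the window:

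- C1D15: *g* = 1. Starts 2 or more days apart cannot coincide.
- C2D1: *g* = 1 or 2. Starts 3 or more days apart cannot coincide.

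**3. Enumeration for three subjects A, B, C.** The named harm is that the *earliest* full-dose day is shared, so that no one has yet been observed at that dose. Any same-day pair is a wider count, because it includes a later pair dosed after another subject has already had the full dose.

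For starts 0/1/2 at C1D15 the sets are {14,15}, {15,16}, {16,17}, giving 2 × 2 × 2 = 8 combinations. The earliest day is shared only when A = B = 15, with 2 choices for C: 2 of 8.

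For starts 0/1/2 at C2D1 the sets are {21,22,23}, {22,23,24}, {23,24,25}, giving 27 combinations. The earliest day is shared when A = B = 22 (3 choices for C), A = B = 23 (3 choices), or A = C = 23 with B = 24 (1). The total is 3 + 3 + 1 = 7 of 27.

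| Starts | C1D15, earliest day shared | C1D15, any pair | C2D1, earliest day shared | C2D1, any pair |
|---|---|---|---|---|
| 0/1/2 | 2 of 8 | 4 of 8 | 7 of 27 | 13 of 27 |
| 0/1/3 | 2 of 8 | 2 of 8 | 6 of 27 | 9 of 27 |
| 0/2/4 | 0 of 8 | 0 of 8 | 3 of 27 | 6 of 27 |
| 0/3/6 | 0 of 8 | 0 of 8 | 0 of 27 | 0 of 27 |

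All three subjects can coincide in only one combination: starts 0/1/2 at C2D1, on day 23.

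**4. Hours on nominal days.** If the earlier infusion stops at clock time *s* and the next subject's infusion starts at clock time *t* on the following day, the gap is 24 − (*s* − *t*) hours. It is below 24 whenever *t* is earlier than *s*. Keeping to nominal visit days therefore does not guarantee the gap.

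**5. Are consecutive-day starts feasible?** Infusion length is not given. Protocol Table 3 says only "If infusion lasts for more than 60 minutes, vital signs should be assessed every 15 minutes". With a 24-hour stop-to-start gap at C1D1, each start slips by one infusion length *L*, so three consecutive-day starts need 2*L* ≤ *W*, where *W* is the daily period in which infusions can start. Assuming *W* = 6, 8 or 10 hours, *L* may be at most 3, 4 or 5 hours.

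**6. Sensitivity to the window anchor.** If each window ran from the previous dose instead (an assumption), the slack would accumulate to 1 + 1 = 2 days at C1D15 and 1 + 1 + 2 = 4 days at C2D1. Same-day dosing would then be possible with starts up to 2 and 4 days apart.

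**7. Size of the dose step.** In SAP Table 1, six of nine sequences reach the full dose on C1D15. Full dose divided by preceding dose: 10/3 = 3.3, 30/3 = 10, 30/5 = 6, 30/10 = 3, 45/5 = 9, 60/3 = 20. These six hold four full-dose levels (10, 30, 45, 60 mg). The table shows neither clearance status nor cohort size. Only 60 mg, the highest level, must have been uncleared when opened.

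**The case against.** The strongest reply is that the rule already covers every infusion. Its purpose refers to each new dose level and its exemption depends on cleared full-dose levels, so a reader could take the gap to apply at the full dose. That reading is possible. It supports stating the point, because the endpoint as written is treatment start and no readable text names the first full dose.

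Text is also missing. In 4.2, the sentence on the DLT period ends in a colon with nothing after it, and Figure 1 is not shown. A gap stated only there cannot be excluded.

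The route that SAP Table 1 lists, C1D15, is premedicated and never lets all three subjects coincide. It needs starts one day apart, with the earlier subject using the window and the later one on time. Priming and intermediate doses, 4 hours' observation, next-day visits and the SC's option to add overnight stays all reduce risk to the individual. None of them holds back the second subject.

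A reader might take 4 of 8 and 13 of 27 as the size of the problem. Those counts include later pairs, so they overstate the named harm. A reader might also extend the point to a single-subject cohort expanded by two. That case mostly does not apply. The added subjects enter after the index subject's trigger event, and their first full dose comes at least 14 days after they start. By then the index subject would normally have had the full dose, unless delayed or discontinued.

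**Conclusion.** The point holds as a gap in the readable wording, for multi-subject cohorts at a full-dose level not yet cleared by the SC. Same-day first exposure is permitted under the natural reading if starts are 1 day apart (C1D15) or 1 to 2 days apart (C2D1). With starts on days 0, 1 and 2, this is 2 of 8 and 7 of 27 in-window combinations. Separately, the interval can fall below 24 hours on nominal days.

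This rests on windows counted from each subject's own C1D1, near-consecutive starts, and no gap being stated in the unreadable text. The figures count calendar combinations and say nothing about how often each would occur.

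A reader might infer that subjects were in fact dosed together, or that three at once was a practical risk. The documents support neither. They give no start dates or cohort sizes. SAP 1.2 describes at most one intermediate dose as tested, and its only sequence with a C2D1 first full dose shows the last two doses in parentheses. No harm is shown. SAP 1.2 also reports that enrollment was stopped, so the point concerns the protocol as written. It merits correction because the consequence is patient safety and the remedy is cheap.

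**What to change.** Add one sentence to Protocol 4.2: for a DL cohort whose full-dose level the SC has not yet safety-cleared, the 24-hour gap, measured from infusion stop to the next same-cohort subject's infusion start, applies at the first full dose (C1D15 or C2D1) as well as at C1D1. Keep the backfill exemption.

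The cost is coordination of infusion times across sites, with shifts of about one day at C1D15 or two at C2D1. For starts 0/1/2, days 14/15/16 or 15/16/17 (C1D15), and at the latest 23/24/25 (C2D1), lie inside the windows, provided clock times keep the 24 hours. If each subject had to wait an extra calendar day, C2D1 on 21/23/25 would still fit. C1D15 on 14/16/18 would put the third subject one day past the window (16 + 1 = 17). That remains well within the 7-day delay per dose that 11.1.7 generally accepts, so DLT evaluability should not be affected.
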